8.2.3. Overview of Planned Other Safety Analyses

The safety analyses will be based on the Safety population, unless otherwise specified.

Table 8 provides an overview of the planned analyses, with further details of data displays being presented in Appendix 13: List of Data Displays.

Table 8 Overview of Planned Other Safety Analyses

Endpoint / Parameter/ Display Type		Abso	olute	Change from B						
	Summary		Summary		Summary		Individual	Sumr	nary	Individual
	Т	F	L	T F		L				
ECG										
All ECG Values for Subjects with a Value of PCI ^[1]			Y							
Abnormal ECG Findings[2]			Y							

NOTES:

- T = Table, F = Figures, L = Listings, Y = Yes display generated, PCI = Potential Clinical Importance
- Summary = Represents TFL related to any summaries (i.e. descriptive statistics) of the observed raw data.
- Individual = Represents FL related to any displays of individual subject observed raw data.
- [1] When QTc data is evaluated for PCI, all of the QTcB, QTcF and QTc collected in the eCFR are considered. Any one of the three meeting the PCI range is identified as an ECG event of PCI..
- [2] When QTc data is evaluated for ECG abnormality, all of the QTcB, QTcF and QTc collected in the eCFR are considered. Any one of the three meeting the abnormality criteria is identified as an abnormal ECG Finding.

8.3. Pharmacokinetic Analyses

8.3.1. Overview of Planned Pharmacokinetic Analyses

PK samples will be drawn on Day 1 (pre-dose, prior to 2nd dose), Days 3 and 5 to coincide with PD measurements (biomarkers) and additionally drawn on Day 3 (5th or 6th dose) at 0.5, 1 (end of infusion), 1.5, 2, 3, 4, 8 and 12 hours post-dose.

Table 9 provides an overview of the planned analyses with full details being presented in Appendix 13: List of Data Displays.

Table 9 Overview of Planned Pharmacokinetic Analyses

Endpoints	Untransformed				Log-Transformed				
	Summary		Individual		Summary		Individual		
	F	T	F	L	F	T	F	L	
DNX Concentrations	Υ	Υ		Υ	Υ	Y			
DNX PK Parameters		Υ		Υ		Y			

NOTES:

- T = Table, F = Figures, L = Listings, Y = Yes display generated.
- Stats Analysis = Represents TFL related to any formal statistical analyses (i.e. modelling) conducted.
- Summary = Represents TFL related to any summaries (descriptive statistics) of the observed raw data.
- Individual = Represents FL related to any displays of individual subject observed raw data.

8.3.2. Drug Concentration Measures

Concentrations of Danirixin (GSK1325756) in blood will be listed and summarised by treatment group, day and nominal time.

Individual blood concentration-time profiles and median/mean profiles by treatment group will be plotted. Each of the figures will contain one plot on the untransformed scale (i.e. a linear plot) and one plot on the log transformed scale (i.e. log-linear plot).

Refer to Appendix 5: Data Display Standards & Handling Conventions (Section 11.5.3 Reporting Process & Standards).

8.3.3. Pharmacokinetic Parameters

8.3.3.1. Deriving Pharmacokinetic Parameters

Pharmacokinetic parameters described in Table 10 will be determined from the concentration-time data, as data permits.

Table 10 Derived Pharmacokinetic Parameters

Parameter	Parameter Description
AUC(0-12)	Area under the concentration-time curve from time zero to the time of the
	last quantifiable concentration (C(t)) will be calculated using the linear

Parameter	Parameter Description
	trapezoidal rule for each incremental trapezoid and the log trapezoidal rule for each decremental trapezoid.
Cmax	Maximum observed concentration, determined directly from the concentration-time data.
tmax	Time to reach Cmax, determined directly from the concentration-time data.
Cavg	Average concentration.

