7.5. Pharmacokinetics

7.5.1. Blood Sample Collection

A blood sample (1-2 mL) for the provision of dried blood spot (DBS) collection and subsequent analysis of DNX concentration, will be collected at the time points indicated in Section 7.1, Time and Events Tables. The actual date and time of each blood sample collection will be recorded. The timing of PK samples may be altered and/or PK samples may be obtained at additional time points to ensure thorough PK monitoring.

Processing, storage and shipping procedures are provided in the Study Reference Manual (SRM).

Blood (DBS) analysis will be performed under the control of Platform Technology and Science – InVivo/ InVitro Translation PTS- IVIVT/ Third Party Resources TPR, GlaxoSmithKline, the details of which will be included in the SRM. Concentrations of DNX will be determined in blood (DBS) samples using the currently approved bioanalytical methodology. Raw data will be archived at the bioanalytical site (detailed in the SRM).

Once the blood has been analyzed for DNX any remaining blood may be analyzed for other compound-related metabolites and the results reported under a separate PTS-IVIVT, GlaxoSmithKline protocol.

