11.5.3. Reporting Process & Standards

Reporting Process			
Software	Software		
The currently support to the currently su	The currently supported versions of SAS and TSCG software will be used.		
Reporting Area			
HARP Server	: US1SALX00259		
HARP Area	: \ARPROD\GSK1325756\MID201023\Final_xx		
QC Spreadsheet : \ARWORK\GSK1325756\MID201023\Final_xx\documents			
Analysis Datasets			

Reporting Process

- Final analysis and IDMC datasets will be created based on Integrated Data Standards Library (IDSL).
- RTF files will be generated for final analysis.

Reporting Standards

General

- The current GSK Integrated Data Standards Library (IDSL) will be applied for reporting, unless otherwise stated:
 - 4.03 to 4.23: General Principles
 - 5.01 to 5.08: Principles Related to Data Listings
 - o 6.01 to 6.11: Principles Related to Summary Tables
 - 7.01 to 7.13: Principles Related to Graphics

Formats

- GSK IDSL Statistical Principles (5.03 & 6.06.3) for decimal places (DP's) will be adopted for reporting of data based on the raw data collected.
- Numeric data will be reported at the precision collected on the eCRF.
- The reported precision from non eCRF sources will follow the IDSL statistical principles but may be adjusted to a clinically interpretable number of DP's.

Planned and Actual Time

- Reporting for tables, figures and formal statistical analyses :
 - Planned time relative to dosing will be used in figures, summaries, statistical analyses and calculation of any derived parameters, unless otherwise stated.
- Reporting for Data Listings:
 - Planned and actual time relative to study drug dosing will be shown in listings (Refer to IDSL Statistical Principle 5.05.1).
 - Unscheduled or unplanned readings will be presented within the subject's listings.
 - Visits outside the protocol defined time-windows (i.e. recorded as protocol deviations) will be included in listings but omitted from figures, summaries and statistical analyses.

Unscheduled Visits

- Unscheduled visits will not be included in summary tables or figures, unless otherwise stated.
 - Unscheduled visits will be included in the maximum toxicity or maximum change from baseline for toxicity tables.
- All unscheduled visits will be included in listings.

Descriptive Summary Statistics		
Continuous Data	Refer to IDSL Statistical Principle 6.06.1	
Categorical Data	N, n, frequency, %	
Reporting of Pharmacokinetic Concentration Data		
Descriptive	Refer to IDSL Statistical Principle 6.06.1	

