11.6.5. Biomarker

11.6.5.1. Biomarkers and Source

SAM	Serum	Nasal Wash	BAL
IL-6, IL-10, IP- 10, IL-8, MPO, NE, IL-1b	Procalcitonin	IL-6, IL-10, IP-10 , IL-8 , MPO , NE , IL-1b	IL-6, IL-10, IP- 10 , IL-8 , MPO , NE , IL- 1b
	C1M, C3M, EL-NE	Neutrophil Cell Counts	
SP-D, sRAGE,	SP-D, sRAGE	SP-D, sRAGE	SP-D, sRAGE

Biomarker

- If a laboratory value which is expected to have a numeric value for summary purposes, has a non-detectable level reported in the database, where the numeric value is missing, but typically a character value starting with '<x' or '>x' (or indicated as less than x or greater than x in the comment field) is present, the number of significant digits in the observed values will be used to determine how much to add or subtract in order to impute the corresponding numeric value.
 - Example 1: 2 Significant Digits = '< x ' becomes x 0.01
 - Example 2: 1 Significant Digit = '> x' becomes x + 0.1
 - Example 3: 0 Significant Digits = '< x' becomes x 1

AUC of Biomarker

- The area under the curve (AUC) to Day 5, Day 45, and PT Day 3 of biomarker as measured by the level of biomarker from biomarkers source:
- The AUC will be calculated as

AUC (0-Day x) =
$$\sum_{0-1} \{ \frac{1}{2} (C_i + C_{i+1}) (t_{i+1} - t_i) \}$$

Where,

C_i = level of biomarker at actual time point i in Day

t_i = actual time of assessment for time point i in Day

i = actual time of assessment in Day (e.g. Day 1, 3, 5, 8, 16, 24, 32, day 45)

I = last i (Day 5, Day 45, or PT Day 3)

- Actual study day will be used for the AUC calculation.
- When baseline value of a biomarker is missing, AUC for the biomarker will be missing.
- When a subject has only baseline value, AUC will be missing.
- When value of a biomarker is missing between visits, there will be no imputation for the missing value, e.g. subject has day 1, 3, 5, 8, 16, 32, 45 values, and day 24 value is missing, day 24's value will not be imputed, AUC will be calculated using day 1,3,5, 8,16, 32, and 45 values.
- When value of a biomarker is missing at the end, last observation carried forward (LOCF) will be used to impute missing value, e.g, subject has day 1, 3, 5, 8, 16, 24, 32 values and day 45 is missing, day 45 value will be imputed using day 32 value (day 45 value will be assumed the same as day 32 value).
- The value of the AUC(0-45) biomarker is missing if there is no assessment beyond week 24.
- The length of time from Baseline to PT Day 3 visit will vary for subjects who prematurely

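### SAP Table 10 labels as AUC(0-12) what it defines as AUC to the last quantifiable sample, takes planned times by default, and gives Cavg no formula

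*SAP*

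**What the plan says.** SAP 8.3.3.1 says the PK parameters "will be determined from the concentration-time data, as data permits". In Table 10 the row labelled AUC(0-12) is described as "Area under the concentration-time curve from time zero to the time of the", continuing "last quantifiable concentration (C(t)) will be calculated using the linear" trapezoidal rule on rising segments and the log rule on falling ones. The whole entry for Cavg is "Average concentration". SAP 8.3.1 has samples "additionally drawn on Day 3 (5th or 6th dose) at 0.5, 1 (end of infusion), 1.5, 2, 3, 4, 8 and 12 hours post-dose".

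On the time basis, SAP 11.5.3 states: "Planned time relative to dosing will be used in figures, summaries, statistical analyses and calculation of any derived parameters, unless otherwise stated". Nothing in SAP 8.3 states otherwise for PK parameters. The overview in SAP Section 11 lists a pharmacokinetic item under Appendix 6, but subsections 11.6.1 to 11.6.6 contain none.

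Where the authors wanted actual time they said so. For biomarker areas, SAP 11.6.5.1 has "Actual study day will be used for the AUC calculation", and the programming note for Figure 4.5 puts individual concentration plots on actual time. The data exist for PK too. Protocol 7.5.1 says "The actual date and time of each blood sample collection will be recorded".

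**The concern.** AUC(0-t) equals AUC(0-12) only when the 12 h sample exists and is quantifiable. If it is missed, the SAP as written reports a shorter area under the 12 h label. No rule says whether to extrapolate, relabel or leave the value missing. Cavg cannot be programmed from the SAP without choosing a numerator and a divisor. The planned-time rule adds error that the recorded times could largely avoid.

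AUC, Cmax and Cavg make up the secondary PK endpoint, and SAP 8.3.4 drops the population PK analysis, so these derived parameters carry the objective. The study ended with 10 subjects randomised 2:2:1, so about 10 × 2/5 = 4 profiles per dose are expected (the actual split is not given). SAP 11.5.3 summarises them by geometric mean and 95% CI. Figure 7.12 plots PK parameters against target-engagement biomarkers, without naming which parameters.

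**Working it through.** The plan gives no AUC value, so there is no stated figure to reproduce. The sizes below are illustrative.

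**Inputs.** Protocol 4.5 gives 1 h infusions every 12 h and IC90 = 707 ng/mL. For 15 mg and 50 mg respectively it projects averages near IC70 and IC90, troughs near IC40 and IC70, and about 1 h and 4 h above IC90. *Assumption:* Hill slope 1, so C_x = IC50 × x/(1 − x). Then IC50 = 707/9 = 78.6, IC70 = 78.6 × 0.7/0.3 = 183 and IC40 = 78.6 × 0.4/0.6 = 52 ng/mL.

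**Profiles.** A two-exponential steady-state curve was fitted separately to each dose. The 15 mg curve has rates 2 and 0.08 per h, mean 183 ng/mL and 0.90 h above IC90. The 50 mg curve has rates 0.6 and 0.12 per h, mean 707 ng/mL and 4.07 h above IC90. The SAP's linear-up/log-down rule was applied at 0, 0.5, 1, 1.5, 2, 3, 4, 8 and 12 h. With complete data the grid error is about 1%: 2,181 against an exact 2,200 ng·h/mL at 15 mg, and 8,579 against 8,484 at 50 mg.

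**Truncation.**

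| Last usable sample | 15 mg, ng·h/mL | 50 mg, ng·h/mL |
|---|---|---|
| 12 h | 2,181 | 8,579 |
| 8 h | 1,934 (−11.3%) | 7,599 (−11.4%) |
| 4 h | 1,590 (−27.1%) | 5,561 (−35.2%) |

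A second 50 mg profile has terminal half-life 7.2 h, from the 36 h stated as five half-lives in Protocol 5.1 (36/5). It loses 12.0% at 8 h and 37.2% at 4 h; it does not reproduce the 1 h above IC90 at 15 mg. With mono-exponential decay the 8-12 h share is 21.6%.

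**Cavg.** Taken as AUC(0-t)/12, it is low by the same percentages. Taken as AUC(0-t)/t, it is high. At 8 h, 0.886 × 12/8 = 1.33 (+33%). At 4 h, 0.729 × 12/4 = 2.19 (+119%, 15 mg) and 0.648 × 12/4 = 1.94 (+94%, 50 mg).

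**Arm level.** One profile low by d among four multiplies the geometric mean by (1 − d)^(1/4).
- 8 h stop: 0.886^(1/4) = 0.970 and 0.880^(1/4) = 0.969, about −3%. In the mono-exponential case 0.784^(1/4) = 0.941, about −6%.
- 4 h stop: 0.729^(1/4) = 0.924 and 0.628^(1/4) = 0.890, about −8% to −11%.

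**Time basis, random errors.** *Assumption:* draw-time SD of 10-15 min up to 4 h and 0.5-1 h later. In 5,000 simulated profiles, subject-level AUC error had SD 3.0% (smaller errors) and 4.9% (larger) on planned times, against 1.1% and 2.0% on actual times. The planned-time mean error was near zero, and its 95% range reached −9% to +10%.

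**Time basis, fixed patterns** (% change against the complete on-time profile):

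| Pattern | 15 mg planned / actual | 50 mg planned / actual |
|---|---|---|
| 1.5 h and 2 h draws 30 min late | −9.7 / +0.7 | −4.7 / 0.0 |
| Draws after 1 h, up to 8 h, all 15 min late | −6.9 / +0.1 | −5.5 / −0.1 |
| 8 h draw 1 h early | +1.1 / 0.0 | +2.9 / −0.3 |
| 1 h draw 15 min late | −8.5 / −6.4 | −1.5 / −2.2 |
| 12 h draw 1 h early | +0.4 / −2.5 | +0.7 / −2.3 |

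The last two rows limit what actual times can do. They cannot restore a missed peak. With an early last draw, the actual-time area stops at 11 h, which is truncation again. The time basis and the upper limit therefore have to be fixed together.

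**The case against.** The stakes are modest. SAP 2.1 makes all analyses descriptive, and 8.3.3.2 plans no formal PK analysis. The qualifier "will be determined from the concentration-time data, as data permits" lets a statistician leave an incomplete profile underived. Listings 40 and 41 show every concentration and parameter, listings carry planned and actual times, and Figure 4.5 plots each subject on actual time. With 10 subjects, a careful reader could spot a truncated or mistimed profile.

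Nothing in the documents shows truncation to be likely. The LLQ is not given, and the projected troughs do not suggest non-quantifiable 12 h values; a missed sample is the more plausible route. A 4 h stop, which gives the largest errors, is not suggested anywhere.

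All of this limits the size of the problem, but visibility in a listing does not correct a summary table whose label and definition disagree. The qualifier is not a rule for a missing 12 h value.

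Three stronger readings are tempting and are not supported:
- *Reported Cavg is wrong.* It has no formula, so neither the size nor the sign of an error can be stated. The supportable point is that it is undefined.
- *A mistimed profile would read as lower exposure than projected.* Random mistiming has mean error near zero; only consistently late draws push AUC down. The SAP also plans no comparison with the dose-justification projection.
- *All reported AUCs are affected.* Complete, on-time profiles are not.

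**Conclusion.** The point stands as a correction of definitions that should be made. Table 10's label and definition disagree, Cavg is undefined, and the time basis for PK parameters defaults to planned time although actual times are available.

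The effect is confined to incomplete or mistimed profiles. Truncation at 8 h understates AUC(0-12) by about 11-12% (22% if mono-exponential), and at 4 h by about 27-37%. Planned times cost about 3-5% SD per subject against 1-2%, without systematic direction unless draws run late. A single 5% timing error moves a four-subject geometric mean by about 1% (1.05^(1/4) = 1.012).

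These sizes rest on a Hill slope of 1, profile shapes fitted to the projections in Protocol 4.5, the assumed draw-time errors, and about four profiles per dose. The documents do not give the Hill slope or the draw-time errors. No hypothesis test is affected.

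**What to change.** In Table 10:
- Define AUC(0-12) as the area over the 12 h dosing interval, using actual elapsed time from the start of infusion.
- Define Cavg = AUC(0-12)/12.
- When the 12 h value is missing or non-quantifiable, report AUC(0-t) under its own label and set AUC(0-12) and Cavg to missing.
- Extrapolate to 12 h only if the last quantifiable sample is at about 8 h or later and a pre-specified terminal-slope criterion (minimum points and fit) is met. The same rule covers a 12 h sample drawn early.

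The limit on extrapolation matters. In illustrative profiles, extrapolating after an 8 h stop leaves an error below 1%. After a 4 h stop, the slope still reflects distribution and AUC(0-12) stays about 9-12% low.

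In SAP 11.5.3, exempt PK parameters from the planned-time rule and keep planned times for by-time summaries and plots.

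The cost is a few SAP sentences and standard software settings, with no new data. The downside is that an occasional AUC(0-12) becomes missing, which is noticeable with about four profiles per dose.

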8.3.3.2. Statistical Analysis of Pharmacokinetic Parameters

No formal statistical analysis of derived pharmacokinetics parameter will be performed.

8.3.4. Population Pharmacokinetic (PopPK) Analyses

Given the small number of subjects enrolled population PK analysis for this study will not be performed.

8.4. Biomarker Analyses

8.4.1. Overview of Planned Biomarker Analyses

The Biomarker analyses will be based on the Influenza Positive Population, unless otherwise specified.

Table 11 provides an overview of the planned Biomarker analyses, with full details of data displays being presented in Appendix 13: List of Data Displays.

Table 11 Overview of Planned Biomarker Analyses

[Endpoint /	Untransformed										
Parameter/ Display		Abso	olute		(Change fro	m Baselin	ie			
Type]	Summary		Indiv	Individual		mary	Individual				
	T	F	F	L	T	F	F	L			
Serum Biomarkers			Υ	Υ							
Nasal wash biomarkers ^[1]			Y	Y							
Nasal SAM strips biomarkers			Y	Y							
BAL Biomarker			Υ	Υ							

NOTES:

- T = Table, F = Figure, L = Listing, Y = Yes display generated.
- Stats Analysis = Represents TFL related to any formal statistical analyses (i.e. modelling) conducted.
- Summary = Represents TFL related to any summaries (i.e. descriptive statistics) of the observed raw data.
- Individual = Represents FL related to any displays of individual subject observed raw data.

[1] includes neutrophil count

8.5. Pharmacodynamic / Biomarker Statistical Analyses

8.5.1. Overview of Planned Pharmacodynamic / Biomarker Analyses

The Pharmacodynamic / Biomarker analyses will be based on the Influenza Positive Population, unless otherwise specified.

Table 12 provides an overview of the planned Biomarker / Pharmacodynamic analyses, with full details of data displays being presented in Appendix 13: List of Data Displays.

Table 12 Overview of Planned Pharmacodynamic / Biomarker Analyses

	Absolute				Change from Baseline			
	Sum	mary	Individual		Summary		Individual	
	Η	F	F	Ш	Т	F	F	L
Biomarkers vs. Biomarkers			Y [1]					
Area under the curve for Serum Biomarkers TTCR			Y [2]					
Area under the curve for Nasal wash biomarkers – TTCR			Y [2]					
Area under the curve for Nasal SAM Strips biomarkers – TTCR			Y [2]					
Area under the curve for BAL biomarkers – TTCR			Y [2]					
Area under the curve for Serum Biomarkers - TTRR			Y [2]					
Area under the curve for Nasal wash biomarkers – TTRR			Y [2]					
Area under the curve for Nasal SAM biomarkers – TTRR			Y [2]		_			
Area under the curve for BAL biomarkers – TTRR	_		Y [2]					

NOTES:

- T = Table, F = Figure, L = Listing, Y = Yes display generated.
- Stats Analysis = Represents TFL related to any formal statistical analyses (i.e. modelling) conducted.
- Summary = Represents TFL related to any summaries (i.e. descriptive statistics) of the observed raw data
- Individual = Represents FL related to any displays of individual subject observed raw data.
- [1] Matrix comparative plot of individual scatter plot of biomarkers vs. biomarkers for Each Biomarker. The x and the y-axis will include Serum, Nasal Wash, Nasal SAM Strips and BAL. Include the Pearson's correlation coefficient and p-value.
- [2] Individual scatter plot of area under the curve biomarkers vs Time to Clinical Response, Time to Respiratory Response.

8.6. Pharmacokinetic / Pharmacodynamic Analyses

Relationships between Danirixin systemic exposure and the following pharmacodynamic measures will be explored graphically:

• Target engagement biomarker: IL-8, respiratory neutrophil cell counts, neutrophil elastase, and myeloperoxidase.

Pharmacokinetic/pharmacodynamic modelling may be attempted to describe any relationship including appropriate models for longitudinal variables versus systemic exposure. Results of PK/PD modelling analysis will be done under a separate Reporting and Analysis Plan and will be reported separately from the main CSR.

8.7. Health Outcome Analyses

8.7.1. Overview of Planned Health Outcome Analyses

The health outcome analyses will be based on the IPP population, unless otherwise specified.

 Table 13
 Overview of Planned Health Outcome Analyses

Endpoints	Absolute				Change from BL			
	Summary		Individual		Summary		Individual	
	F	T	F	L	F	Τ	F	L
KATZ ADL				Y		Y		
Flu PRO		Υ		Υ		Υ		

NOTES:

- T = Table, F = Figures, L = Listings, Y = Yes display generated.
- Summary = Represents TFL related to any summaries (descriptive statistics) of the observed raw data.
- Individual = Represents FL related to any displays of individual subject observed raw data.

9. VIROLOGY ANALYSES

9.1. Overview of Planned Virology Analyses

The virology analyses will be based on the IPP population, unless otherwise specified.

Table 14 provides an overview of the planned analyses, with full details being presented in Appendix 13: List of Data Displays.

Table 14 Overview of Planned Virology Analyses

Endpoints	Absolute Change from BL							
	Summary		Individual		Summary		Individual	
	F	Т	F	L	F	T	F	L
Influenza Viral Load by qRT- PCR				Y		Y [2,3]	Υ[1,2,3]	
Influenza Viral Load by qVC				Υ		Y [2,4]	Y [1,2,4]	

Endpoints		Abs	olute		Change from BL				
	Summary		Individual		Summary		Individual		
	F	Т	F	L	F	Т	F	L	
Resistance Associated Mutations Detected in the NA Gene by Subtype Nasopharyngeal		Υ		Y					
Resistance Associated Mutations Detected in the HA Gene by Subtype Nasopharyngeal		Y		Y					
Proportion of Subjects - Positive Other Viruses by Multiplex		Y							

NOTES:

- T = Table, F = Figures, L = Listings, Y = Yes display generated.
- Stats Analysis = Represents TFL related to any formal statistical analyses (i.e. modelling) conducted.
- Summary = Represents TFL related to any summaries (descriptive statistics) of the observed raw data.
- Individual = Represents FL related to any displays of individual subject observed raw data.
- [1] Change from baseline plot for nasopharyngeal
- [2] For nasopharyngeal
- [3] Overall virus and by subtype
- [4] For subjects culture positive at baseline, if warranted.

